### **4.1. Inclusion Criteria**

Subject eligibility should be reviewed and documented by an appropriately qualified member of the investigator's study team before subjects are included in the study.

Subjects must meet all of the following inclusion criteria to be eligible for enrollment into the study:

1. Evidence of a personally signed and dated informed consent document (ICD) indicating that the subject has been informed of all pertinent aspects of the study.
2. Healthy male and female adults aged 65 to 85 years at enrollment (signing of the ICD) as determined by medical history, physical examination, and the clinical judgment of the investigator to be eligible for the study. Subjects with preexisting chronic medical conditions determined to be stable may be included.
3. Male subjects able to father children must agree to use a highly effective method of contraception from the time of informed consent through at least 28 days after the last dose of investigational product.
4. Female subjects who are not of childbearing potential (ie, meet at least 1 of the following criteria):
  - Have undergone hysterectomy and/or bilateral oophorectomy;
  - Have medically confirmed ovarian failure; or
  - Achieved postmenopausal status, defined as cessation of regular menses for at least 12 consecutive months with no alternative pathological or physiological cause; status may be confirmed by having a serum follicle-stimulating hormone (FSH) level confirming the post menopausal state.
5. Availability for the entire duration of the study, and able to comply with scheduled visits, treatment plan, and study procedures, including completion of the e-diary.
6. Ability to be contacted by telephone during study participation.

### **4.2. Exclusion Criteria**

Subjects with any of the following characteristics/conditions will not be included in the study:

1. Previous administration of an investigational *C difficile* vaccine or *C difficile* mAb therapy.
2. Proven or suspected prior episode of CDAD. Please refer to the study reference manual (SRM) for additional guidance.
3. Unstable chronic medical condition or disease requiring significant change in therapy or hospitalization for worsening disease within 8 weeks before receipt of investigational product.
4. Serious chronic medical disorders, including metastatic malignancy, severe chronic obstructive pulmonary disease (COPD) requiring supplemental oxygen, end-stage renal disease with or without dialysis, clinically unstable cardiac disease, or any other disorder that in the investigator's opinion precludes the subject from participating in the study.
5. Bleeding diathesis or condition associated with prolonged bleeding time that may contraindicate intramuscular injection, including subjects taking anticoagulant, antiplatelet, and/or antithrombotic agents except for low-dose daily aspirin ( $\leq 325$  mg/day) within 30 days before enrollment until 1 month after the last vaccination.
6. Any contraindication to vaccination or vaccine components, including previous anaphylactic reaction to any vaccine or vaccine-related components.
7. Subjects with congenital or acquired immunodeficiency disorders, or subjects with rheumatologic disorders or other illnesses requiring chronic treatment with known immunosuppressant medications, including mAbs, within a year of enrollment or the use of systemic corticosteroids for  $\geq 7$  days within 90 days prior to enrollment through conclusion of the study (eg,  $\geq 10$  mg/day of prednisone for  $\geq 7$  days).
8. Active or treated leukemia or lymphoma or underlying bone marrow disorder such as myelodysplasia, myeloma, or myeloproliferative disorder, treated within the past year, or any history of bone marrow transplant.
9. Malignancy that required treatment with chemotherapy (including the use of adjunctive and hormonal therapy), immunotherapy, radiation therapy, or antineoplastic target therapies within the past 24 months.
10. Subjects who received oral or parenteral antibiotics within 1 month before enrollment. Topical antibiotics are allowed.
11. Receipt of blood products or immunoglobulins (including mAbs) within 6 months before enrollment through conclusion of the study.
12. Participation in other studies involving investigational drug(s) within 30 days prior to study entry up to and including Visit 12. Participation in purely observational studies is acceptable.

13. Subjects who are investigational site staff members directly involved in the conduct of the study and their family members, site staff members otherwise supervised by the investigator, or subjects who are Pfizer employees directly involved in the conduct of the study.
14. Females of childbearing potential; males of child-fathering potential who are unwilling or unable to use a highly effective method of contraception as outlined in this protocol for at least 28 days after the last dose of investigational product.
15. Residence in a nursing home or other long-term care facility, or requirement for semiskilled nursing care or assisted living. An ambulatory subject who lives in an autonomous manner in a retirement home or village is eligible for the trial.
16. A known infection with human immunodeficiency virus (HIV), hepatitis B virus (HBV), and/or hepatitis C virus (HCV).
17. Other severe acute or chronic medical or psychiatric condition or laboratory abnormality that may increase the risk associated with study participation or investigational product administration or may interfere with the interpretation of study results and, in the judgment of the investigator, would make the subject inappropriate for entry into this study.

#### **4.3. Inclusion Criteria for the Extension Stage**

Subject eligibility should be reviewed and documented by an appropriately qualified member of the investigator's study team before subjects are included in the extension stage.

Subjects must meet all of the following inclusion criteria to be eligible to enter the extension stage:

1. Evidence of a personally signed and dated ICD addendum indicating that the subject has been informed of all pertinent aspects of the extension stage of the study.
2. Healthy male and female adults as determined by medical history, physical examination, and the clinical judgment of the investigator to be eligible for the study. Subjects with preexisting chronic medical conditions determined to be stable may be included.
3. Receipt of all 3 doses of *C difficile* vaccine (100- $\mu$ g or 200- $\mu$ g antigen dose level) in the original portion of the study.
4. Male subjects able to father children must agree to use a highly effective method of contraception from the time of informed consent through at least 28 days after the fourth dose.
5. Female subjects who are not of childbearing potential (ie, meet at least 1 of the following criteria):
  - Have undergone hysterectomy and/or bilateral oophorectomy;

- Have medically confirmed ovarian failure; or
- Achieved postmenopausal status, defined as cessation of regular menses for at least 12 consecutive months with no alternative pathological or physiological cause; status may be confirmed by having a serum FSH level confirming the postmenopausal state.

6. Availability for the entire duration of the study, and able to comply with scheduled visits, treatment plan, and study procedures, including completion of the e-diary.
7. Ability to be contacted by telephone during study participation.

#### **4.4. Exclusion Criteria for the Extension Stage**

Subjects with any of the following characteristics/conditions will not be eligible to enter the extension stage:

1. Subjects originally randomized to placebo in either dosing regimen during the original portion of the study.
2. Subjects who have already completed Visit 9 prior to study unblinding.
3. Previous administration of a *C difficile* mAb therapy.
4. Proven or suspected prior episode of CDAD. Please refer to the SRM for additional guidance.
5. Unstable chronic medical condition or disease requiring significant change in therapy or hospitalization for worsening disease within 8 weeks before receipt of investigational product.
6. Serious chronic medical disorders, including metastatic malignancy, severe COPD requiring supplemental oxygen, end-stage renal disease with or without dialysis, clinically unstable cardiac disease, or any other disorder that in the investigator's opinion precludes the subject from participating in the study.
7. Bleeding diathesis or condition associated with prolonged bleeding time that may contraindicate intramuscular injection, including subjects taking anticoagulant, antiplatelet, and/or antithrombotic agents except for low-dose daily aspirin ( $\leq 325$  mg/day) within 30 days before until 1 month after the fourth dose.
8. Any contraindication to vaccination or vaccine components, including previous anaphylactic reaction to any vaccine or vaccine-related components.
9. Subjects with congenital or acquired immunodeficiency disorders, or subjects with rheumatologic disorders or other illnesses requiring chronic treatment with known immunosuppressant medications, including mAbs, within a year of enrollment or the use of systemic corticosteroids for  $\geq 7$  days within 90 days prior to enrollment through conclusion of the study (eg,  $\geq 10$  mg/day of prednisone for  $\geq 7$  days).

10. Active or treated leukemia or lymphoma or underlying bone marrow disorder such as myelodysplasia, myeloma, or myeloproliferative disorder, treated within the past year, or any history of bone marrow transplant.
11. Malignancy that required treatment with chemotherapy (including the use of adjunctive and hormonal therapy), immunotherapy, radiation therapy, or antineoplastic target therapies within the past 24 months.
12. Subjects who received oral or parenteral antibiotics within 1 month before the fourth dose. Topical antibiotics are allowed.
13. Receipt of blood products or immunoglobulins (including mAbs) within 6 months before enrollment through conclusion of the study.
14. Participation in other studies involving investigational drug(s) within 30 days prior to study entry up to and including Visit 12. Participation in purely observational studies is acceptable.
15. Subjects who are investigational site staff members directly involved in the conduct of the study and their family members, site staff members otherwise supervised by the investigator, or subjects who are Pfizer employees directly involved in the conduct of the study.
16. Females of childbearing potential; males of child-fathering potential who are unwilling or unable to use a highly effective method of contraception as outlined in this protocol for at least 28 days after the fourth dose.
17. Residence in a nursing home or other long-term care facility, or requirement for semiskilled nursing care or assisted living. An ambulatory subject who lives in an autonomous manner in a retirement home or village is eligible for the trial.
18. A known infection with HIV, HBV, and/or HCV.
19. Other severe acute or chronic medical or psychiatric condition or laboratory abnormality that may increase the risk associated with study participation or investigational product administration or may interfere with the interpretation of study results and, in the judgment of the investigator, would make the subject inappropriate for vaccination with the fourth dose.

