Adults above the age of 65 years are at increased risk for CDAD, particularly in the healthcare setting, and the likelihood of severe infection among adults similarly increases with age. It is anticipated that the *C difficile* vaccine will ultimately be evaluated for efficacy and safety in an older target population, whose ability to mount an immune response may be impaired: This may influence the selection of an optimal vaccination regimen to ensure short- and long-term protection.

To date, there is no vaccine available to prevent CDAD. Investigational vaccines are in clinical development, but none is licensed. A vaccine consisting of formalin-inactivated TcdA and TcdB is currently in Phase 3 clinical development. Also, a Phase 2 study with a recombinant protein vaccine candidate incorporating truncated portions of TcdA and TcdB has recently started.

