#### **2.1.3. Secondary Immunogenicity Objectives**

- To describe the immunogenicity of 2 antigen dose levels (100 µg and 200 µg total toxoid) of *C difficile* vaccine when administered in a 3-dose regimen (either Days 1, 8, and 30 or Months 0, 1, and 6) to healthy adults aged 65 to 85 years, as measured by *C difficile* toxin A- and toxin B-specific neutralizing antibody levels at multiple time points following vaccination.
- To describe the kinetics of the immune response in healthy adults aged 65 to 85 years for up to 12 months following the administration of 3 doses of *C difficile* vaccine.
- To describe the immunogenicity of a fourth dose of *C difficile* vaccine as measured by *C difficile* toxin A- and toxin B-specific neutralizing antibody levels at multiple time points following vaccination.
- To describe the kinetics of the immune response in healthy adults aged 65 to 85 years for up to 36 months following the administration of a fourth dose of *C difficile* vaccine.

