## **5.2. Blinding of Site Personnel**

In this observer-blinded study, the study staff dispensing and administering the vaccine will be unblinded, but all other site study personnel, including the principal investigator and the subject, will be blinded during the vaccination periods of the study.

Following the third interim analysis (when Month 7 [after the first dose] data are available from all continuing subjects), site personnel will be unblinded to vaccine assignments for the first 3 doses. This will enable site personnel to identify subjects eligible to enter the extension stage. During the extension stage, site personnel (excluding the study staff dispensing and administering the vaccine) will be blinded to vaccine allocation at the fourth dose until Visit 12 (6 months after the fourth dose).

The principal investigator will assign the responsibility of unblinded dispenser and unblinded administrator to persons who will not participate in the evaluation of any study subject. More than 1 unblinded dispenser/administrator may be assigned per site. A member of the study site staff or clinic pharmacy should fulfill this role. Contact between the unblinded dispenser and study subjects should be kept to a minimum. The investigator, study coordinator, and any site staff other than the unblinded dispenser/administrator must not be allowed to know the investigational product assigned to any study subject and must not be allowed to see the investigational product container contents.

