## **5.3. Blinding of the Sponsor**

Those study team members who are involved in ensuring that protocol requirements for investigational product handling, allocation, and administration are fulfilled at the site will be unblinded for the duration of the study. All other study team members will remain blinded to vaccine assigned/received at Doses 1, 2, and 3 until the third interim analysis. Those study team members will also be blinded to vaccine assigned/received at Dose 4 until Visit 12 (6 months after the fourth dose). Laboratory personnel performing the immunologic assays will remain blinded to vaccine assigned/received throughout the study. Certain sponsor personnel not involved in the conduct of the study will review unblinded data as defined in an internal review committee (IRC) charter per Pfizer standard operating procedures (SOPs). In addition to the IRC members, an unblinded statistician, an unblinded physician, and an unblinded clinical scientist, who are not part of the study team, will be assigned to work with an external independent statistical center supporting the IRC and external data monitoring committee (E-DMC) review activities.

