### **5.8.2. Prohibited Concomitant Vaccinations, Medications, and Blood Products**

Unless considered medically necessary, no vaccines (licensed or investigational) other than study vaccine should be administered between signing the ICD and 1 month after the third vaccination (Visit 6 [Month 2] for subjects on the Day 1, 8, and 30 regimen and Visit 7 [Month 7] for subjects on the Month 0, 1, and 6 regimen) or from the time of the fourth dose until Visit 11 (Day 30 after the fourth dose). Whenever possible, any nonstudy vaccine that is considered medically necessary should be administered at least 28 days after, or at least 28 days prior to, administration of study vaccine. Note one exception: licensed nonlive influenza vaccine may be administered at least 14 days after, or at least 14 days prior to, the administration of study vaccine.

Immunosuppressive therapy is prohibited throughout the study; this includes chemotherapy agents or immune-modifying drugs, the latter including, but not limited to, disease-modifying antirheumatic drugs (DMARDs) such as methotrexate and the tumor necrosis factor antagonists, and immune response modifiers such as, but not limited to, ustekinumab. Use of systemic corticosteroids ( $\geq 10$  mg/day of prednisone or equivalent) for  $\geq 7$  days is prohibited within 90 days prior to enrollment through the conclusion of the study.

Any blood products, including immunoglobulin, are also prohibited throughout the course of the study.

Prophylactic antipyretics and other pain medication to prevent symptoms associated with investigational product administration are not permitted. However, if a subject is taking a

permitted medication (according to Section 5.8.3) for another condition, even if it may have antipyretic or pain-relieving properties, it should not be withheld prior to study vaccination.

An e-diary will be used to capture the use of antipyretics/pain medication to treat local reactions and systemic events for 7 or 14 days (dependent upon assigned vaccination regimen) following the first vaccination and 14 days following the second and third vaccinations as described in [Section 7.1.1](#). For subjects entering the extension stage, the e-diary will capture the use of antipyretics/pain medication to treat local reactions and systemic events for 14 days after the fourth dose as described in [Section 7.1.1](#).

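### Extension-stage titers run to Visit 17, but an outside C difficile vaccine received after Visit 12 would be permitted, unrecorded and left in the persistence summaries

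*Protocol*

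**What the plan says.** For Dose 4, one secondary objective in Protocol 2.1.3 is "To describe the kinetics of the immune response in healthy adults aged 65 to 85 years for up to 36 months following the administration". Sampling follows at Months 6, 12, 18, 24, 30 and 36 after Dose 4, which are Visits 12 to 17 (2.2.3, 7.2, extension Schedule of Activities).

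The restrictions that could protect those titers end at different times:

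- Extension exclusion 14 (Protocol 4.4) bars "Participation in other studies involving investigational drug(s) within 30 days prior to study entry up to and including Visit 12".
- Protocol 5.8.2 bars other vaccines, licensed or investigational, unless medically necessary. In the extension this runs "or from the time of the fourth dose until Visit 11 (Day 30 after the fourth dose".
- Protocol 5.8.1 and SAP 3.6.3 record non-study vaccines and concomitant medications only to Visit 11.
- Blood products and immunoglobulins, including mAbs, are barred to study conclusion (4.4, exclusion 13), and immunosuppressants are barred throughout (5.8.2).

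Protocol 1.2.2 acknowledges competing products: "A vaccine consisting of formalin-inactivated TcdA and TcdB is currently in Phase 3 clinical development". It also mentions a second candidate in Phase 2.

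**The concern.** A second vaccine against the same two toxins would raise exactly the antibodies that the extension measures. The plan guards late titers against passive antibody and immunosuppression to the end of the study, but not against active immunization with the same antigens. A titer raised by another product would then be reported as persistence of this one. Because non-study vaccines are no longer recorded by then, the sponsor might have no means of seeing that it had happened. What is at stake is the accuracy of the Month 12 to Month 36 GMCs, GMFRs, fold-rise proportions and threshold proportions.

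**Working it through.** **1. Cut-offs side by side**

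| Item | Source | Ends at |
|---|---|---|
| Antibody sampling | Protocol 2.2.3, 7.2 | Visit 17 (Month 36) |
| Bar on blood products, immunoglobulins, mAbs | Protocol 4.4 #13 | Study conclusion |
| Bar on other investigational-drug studies | Protocol 4.4 #14 | Visit 12 (Month 6) |
| Bar on non-study vaccines | Protocol 5.8.2 | Visit 11 (Day 30) |
| Recording of non-study vaccines and medications | Protocol 5.8.1, SAP 3.6.3 | Visit 11 (Day 30) |

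Visits 13, 14, 15, 16 and 17 follow the last relevant bar, so five of the six visits from Month 6 to Month 36 are exposed.

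**2. Following one hypothetical subject vaccinated elsewhere at Month 9**

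- Neither 4.4 #14 nor 5.8.2 applies any longer. Exclusion 14 is also absent from the extension withdrawal criteria in 6.5 (inclusion 1, 6, 7; exclusion 1, 4, 15, 19).
- The procedures for Visits 13 to 17 (6.3.5 to 6.3.9) ask about ongoing AEs and events within 48 hours of a blood draw, not about vaccines.
- SAP 7.2 removes subjects for major protocol violations, with a prohibited vaccine as an example. This vaccine is not prohibited, so there is no violation.
- The extension evaluable set (SAP 4.1) needs eligibility at rerandomization, Dose 4 as randomized, a Visit 10 sample and no major violation. The subject stays in.
- The mITT set (SAP 4.2) needs randomization and one valid result. The subject stays in.
- SAP 5.3.1 and 6.2.1 contain no rule that drops titers after an outside vaccination.

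**3. Size of the effect**

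The documents give no contamination rate, so a range is assumed. If a share q of a group has its titer multiplied by F, the mean log10 titer rises by q × log10(F) and the GMC is multiplied by F^q. The proportion at or above a threshold rises by at most q.

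For F, the only figures available are the Phase 1 fold rises one month after Dose 3 in the 65- to 85-year cohort, aluminum hydroxide groups (Protocol 1.2.3): 42.73 to 80.66 for toxin A and 136.12 to 484.14 for toxin B. They are three-dose rises from the pre-Dose 1 baseline. Extension subjects have already had three or four active doses, so these serve only as an upper range.

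| q | Toxin A: GMC factor (log10 shift) | Toxin B: GMC factor (log10 shift) |
|---|---|---|
| 1% | 1.038 to 1.045 (0.016 to 0.019) | 1.050 to 1.064 (0.021 to 0.027) |
| 2% | 1.078 to 1.092 (0.033 to 0.038) | 1.103 to 1.132 (0.043 to 0.054) |
| 5% | 1.207 to 1.245 (0.082 to 0.095) | 1.278 to 1.362 (0.107 to 0.134) |

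**4. Comparison with sampling error**

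Protocol Table 7 uses 1.96 × SD / √n. For SD 0.50 and n = 183 this gives 0.072, as printed. With 1:1 rerandomization (Protocol 1.2.3) and every subject entering, an arm has at most 183 / 2 = 91.5 subjects, and √91.5 = 9.566. The SDs come from the Table 7 footnote (Day 37 and Month 7 in the Phase 1 study; assumed to carry over to late visits):

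- Toxin A, SD 0.41 to 0.62: half-width 0.084 to 0.127 log10.
- Toxin B, SD 0.78 to 1.40: half-width 0.160 to 0.287 log10.

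At q = 2% (0.02 × 91.5 = 1.8 subjects) the largest shifts, 0.038 and 0.054, are less than half the narrowest half-widths, 0.084 and 0.160. At q = 5% (4.6 subjects) the toxin A shift of 0.082 to 0.095 becomes comparable to the half-width. Fewer entrants would widen the intervals.

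**The case against.** The strongest reply is that the route is improbable. Protocol 1.2.2 says that no C difficile vaccine is licensed, so exposure would normally mean joining another sponsor's trial. Every extension subject has already had three active doses, and this trial itself refuses prior recipients of such vaccines (4.2, exclusion 1); others may do the same. The pipeline statement rests on references dated December 2014 and January 2015, which do not show that those trials would be recruiting, or would take these subjects, years later. The endpoints are secondary and descriptive, and the fold rises in the working overstate a likely boost in primed subjects. All of this stands, and it is why the point is small. It does not close the gap, because nothing in the plan would detect or handle the event if it occurred.

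A reader might go further, since the Dose 4 blind also ends at Visit 12, and infer that subjects would know their arm, that Dose 4 placebo recipients would seek another vaccine, and that the Dose 4 effect would shrink. The documents do not support this. Under 5.2, site personnel "will be blinded to vaccine allocation at the fourth dose until Visit 12 (6 months after the fourth dose"; under 5.3, "Those study team members will also be blinded to vaccine assigned/received at Dose 4 until Visit 12 (6 months after the fourth dose". Section 5.4 gives allocation access to site personnel. For subjects, 5.2 says only that blinded persons, "including the principal investigator and the subject, will be blinded during the vaccination periods of the study"; what they are told later is unspecified. Nothing supports uptake that depends on the arm. SAP 5.2.2 and 6.2.1 plan summaries by vaccine group, with no between-arm immunogenicity contrast to shrink.

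Nor does the gap show that the blind should last to Visit 17. Visit 12 is where active SAE reporting closes (8.2), which makes it a recognizable place to end the blind, and "Laboratory personnel performing the immunologic assays will remain blinded to vaccine assigned/received throughout the study".

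**Conclusion.** The gap is real. After Visit 12 the plan permits another toxin A/B vaccine, does not record it, and keeps the resulting titers in both analysis sets at five persistence visits. It is also uneven with the plan's own bar on immunoglobulins and mAbs, which runs to study conclusion.

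The practical size is small. At 1% contamination the GMC is inflated by about 4% to 6%, and at 2% by about 8% to 13%. These figures assume the Phase 1 three-dose fold rises as an upper range. Both lie inside the sampling error of an arm of at most about 91 subjects, and only at about 5% would the toxin A bias match that error. The contamination rates are assumptions, and the true rate is probably low. The primary endpoints at Day 37 and Month 7 are unaffected. This is a cheap improvement to the persistence analysis, not a defect that threatens the trial's conclusions.

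**What to change.** - **Recording.** In Protocol 5.8.1 and the extension Schedule of Activities, record any non-study C difficile vaccine or mAb, and any participation in a C difficile vaccine study, with dates, through Visit 17. Without this, neither a bar nor an exclusion rule can be applied. It also covers mAbs, which are barred to study end although medication recording stops at Visit 11.
- **Analysis.** In SAP 4.1, 4.2 and 5.3.1, exclude the subject's titers from the date of receipt onward in both the evaluable and mITT analyses, and keep the earlier ones. State this at the level of the titer. Classing receipt as a major violation would remove the whole subject from the evaluable set and would do nothing in the mITT set, which has no violation criterion.
- **Consistency.** Reconcile the Visit 12 cut-off in 4.4 #14 and the Visit 11 cut-off in 5.8.2 with the 36-month objective and with the immunoglobulin and mAb bar that runs to study conclusion.

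The cost is a protocol and SAP amendment, one extra CRF question at Visits 12 to 17, and the loss of a few late titers if the event occurs.
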